APPENDIX H: PARTICIPATING INVESTIGATORS AND INSTITUTIONS

A complete list of participating investigators and institutions where study activities are conducted will be distributed under separate cover.

APPENDIX I: ETHICS COMMITTEE LIST

A complete list of participating Ethics Committee and the Chairperson(s) will be distributed under separate cover.

APPENDIX J: LABELING

Labeling for all market approved system components can be found with each package insert. Manuals can be found on <http://manuals.medtronic.com>.

APPENDIX K: BIBLIOGRAPHY

A complete bibliography, summary of relevant literature, and summary and results of previous clinical investigations is provided in the Investigator's Brochure. The Investigator's Brochure is available upon request.

APPENDIX L: ADDITIONAL INFORMATION FOR CENTERS BY COUNTRY

Regulations for the conduct of clinical trials vary by country. Required information for centers in each country, such as detailed sponsor contact information, names of monitors, detailed CRF instruction, etc. not outlined in the Clinical Investigational Plan will be provided under separate cover.

APPENDIX M: PREVIOUS CLINICAL INVESTIGATIONS

A summary and results from the Adaptive CRT study, which is the clinical study evaluating the AdaptivCRT algorithm, are provided in the Investigator's Brochure. The Investigator's Brochure is available upon request.

APPENDIX P: DOCUMENT CHANGE HISTORY

Revision	Description of Change	Author
1.0	First issue	██████████ ██████████
2.0	
 1. General: 
 a. Updated information related to sponsor contact, Core laboratory, Steering Committee to reflect the current situation b. Updated availability of study related documents to the current situation c. Updated regulatory requirements to reflect the current situation d. Used the wording in the device manuals to explain the programming in the 2 arms e. Corrected typo's 2. Paragraph 1.1: Study purpose and description 
 a. Used the wording in the device manuals to explain the programming in the 2 arms b. Removed sentence referring to the number of CRT systems in the study as not aligned with the study change to enroll 3500 randomized subjects 3. Paragraph 1.2: Study scope 
 a. Aligned the text with the study change: randomization increase from 3000 to 3500 randomized subjects, an increase of participating sites from 200 to approximately 250, and an increase in study duration b. Added Russia to the participating regions 4. Paragraph 2: Background and justification 
 a. Updated with analyses results and aCRT related manuscripts published since b. Updated aCRT study post-hoc sub-analysis results table 5. Paragraph 3.1: System description and intended use 
 a. Removed the name of the CRT devices used in the study, as the study is about the aCRT algorithm, not about the devices itself. All CRT devices used in the study are commercially available. 6. Paragraph 4: Regulatory compliance 
 a. Updated local laws and regulations to the current situation 7. Paragraph 6.1: Site activation 
 a. Added clarity regarding study training for site personnel 8. Paragraph 6.2: Equipment requirements 
 a. Updated computer requirements to be compatible with the current data base 9. Paragraph 6.3: Data collection 	[name]

Revision	Description of Change	Author
	
 a. Explained acronyms b. Added cardiovascular medications which are recommended for heart failure treatment according to the current guideline 10. Paragraph 6.4: Patient Informed Consent process 
 a. Due to regional regulation differences, added “per local requirements” to the informed consent sign off possibility of a legally authorized representative or guardian 11. Paragraph 6.5: Enrollment 
 a. Added the need to document subject’s participation in the source docs, per current regulations 12. Paragraph 6.6: Baseline 
 a. Changed names of medication to CV medication to also include newly guideline recommended CV medication 13. Paragraph 6.8: Randomization 
 a. Table Programming requirements: Corrected and updated programming requirements according to the current available devices, added recommended programming 14. Paragraph 6.9: Scheduled follow-up visits 
 a. Added follow-up visit windows to table 7 to implement the longer participation of some patients 15. Paragraph 8.4: Adverse event records and reporting requirements 
 a. Added the need for source docs for endpoint adjudication b. Updated tables to the current local reporting requirements 16. Paragraph 10.3: Procedures for termination or suspension 
 a. Added sentence to implement new MDT CIP requirements 17. Paragraph 11.2: Study design 
 a. Added stratification by NYHA class: this was implemented from the start of the study, on request of the Steering Committee. b. Updated timelines for interim analyses based on the current actuals 18. Paragraph 11.3: Primary objective 
 a. Updated sample size rationale to align with the study change (increase randomized subjects from 3000 to 3500) 19. Paragraph 11.5: Secondary and ancillary objectives 
 a. Changed type of regression model 20. Paragraph 13: Warranty/insurance information 
 a. Added Russia b. Updated insurance sections according to current local regulations 21. Paragraph 15: Required records and reports 
 a. Updated according to current local regulations 22. Appendix A: 	

Revision	Description of Change	Author
	
a. Removed "draft" as the Case Report Forms are final23. Appendix E: Study overview
a. Aligned with CIP V2.024. Updated appendix H, I, to the actual status25. Updated appendix O with new references

1 VERSION HISTORY

Version	Version Date	Summary of Changes	Author(s)/Role
1.0	30 SEP 2015	
 Not Applicable, New Document 	██████████, Project Statistician
2.0	29 APR 2016	
 'Version History' is added. For secondary objective #2 (intervention for heart failure decompensation) and #4 (incidence of atrial fibrillation), the primary analysis in the presence of competing risk is changed into the Cox regression while the Fine-Gray regression becomes a secondary analysis. The subsequent sensitivity/subgroup/ancillary analyses are changed as well into the framework of Cox regression. 	██████████, Project Statistician
3.0	15 NOV2021	
 Removed conditional disengagement date from calculation of follow-up time, as it is an administrative date and does not reflect patient contact For frailty models used in analysis of primary objective and secondary objective #1, added example code to specify site-level random effects from a gamma distribution, rather than the default lognormal 	██████████, Project Statistician

2 PURPOSE

This Statistical Analysis Plan (SAP) has been designed to document, before data are analyzed, the rationale for the study design, and the planned analyses that will be included in study reports. This SAP does not limit the analysis in reports, and additional analysis of the study data beyond this plan is expected.

This SAP is developed based on Version 1 of the AdaptResponse Clinical Investigation Plan (CIP) dated April 1, 2014.

3 RATIONALE FOR STUDY DESIGN

The study design and rationale can be found in the CIP. AdaptResponse is a prospective, randomized, controlled, interventional, single-blinded, multi-center, post-market, global Cardiac Resynchronization Therapy (CRT) in heart failure (HF) clinical study. The purpose of this clinical study is to test the hypothesis that market released CRT devices which contain the AdaptivCRT® (aCRT) algorithm have a superior outcome compared to standard CRT devices in CRT indicated patients with normal atrio-ventricular (AV) conduction and left bundle branch block (LBBB).

Following enrollment and baseline assessment, eligible subjects will be implanted with a CRT system containing the aCRT algorithm and randomized in a 1:1 fashion to either treatment (aCRT ON) or control (aCRT OFF) groups. **aCRT ON** means CRT therapy with ambulatory optimization and preferential LV-only pacing; **aCRT OFF** means standard bi-ventricular CRT therapy. The randomization will be stratified by two factors: site and NYHA class at enrollment. The primary objective is to compare the incidence of the combined endpoint of all-cause mortality and intervention for heart failure decompensation between the aCRT ON and aCRT OFF groups. Because the event rate is expected to be relatively low, the study utilizes an “event-driven” design that requires a review of accumulating endpoint events during the trial to possibly modify enrollment goal and follow-up duration in order to maintain study power. Study subjects will be followed until the required number of endpoint events is reached and/or a decision by Medtronic, Ethics Committee, or regulatory authority, whichever occurs first.

4 DESCRIPTION OF ANALYSIS

4.1 General

Medtronic employed statisticians will perform the statistical analyses described in this SAP. Interim analyses will be performed by a Medtronic statistician other than the lead statistician for the study. The lead study statistician will be blinded to all interim analyses.

All tests of treatment effects will be conducted in order to preserve an overall two-sided alpha level of 0.05 unless otherwise stated. An Intention-to-Treat analysis will be performed and will serve as the primary analysis for all objectives in this study. The Intention-to-Treat cohort will include all randomized subjects.

4.1.1 Subject Characteristics at Enrollment and Baseline

A number of subject characteristics recorded on the enrollment and baseline case report forms (CRFs) will be summarized in tables for all the study subjects. **Table 1** lists these characteristics:

Table 1: Subject characteristics in enrollment and baseline forms

CRFs	Subject Characteristics
Enrollment	Gender PR interval QRS duration Left ventricular ejection fraction (LVEF) NYHA class
Baseline	Age Physical exam status Cardiac disease classification Current HF symptoms status Blood measurements Medical history

For continuous variables, descriptive statistics including mean, standard deviation, median, the first quartile and third quartile, minimum and maximum will be presented; for categorical variables, counts and percentages will be given. Subject characteristics will also be summarized by treatment (aCRT ON and aCRT OFF) and NYHA class at enrollment (II, III and IV).

4.1.2 Special Considerations

4.1.2.1 Analysis Blinding

It is planned that Medtronic employed statisticians will perform all statistical analyses. Interim analyses will be performed by the unblinded Medtronic statistician of the study. The lead study statistician will be blinded to all interim analyses. The unblinded statistician will keep results strictly confidential per the DMC charter during the study.

4.1.2.2 ECG Core Lab vs. Site-Determined ECG Data

Per CIP section 1.3, the ECG Core Lab will review all baseline ECGs for presence of LBBB and normal AV conduction, and feedback on accuracy rates will be presented to the Steering Committee and to the sites. However, analyses that involve PR interval, QRS duration and LBBB diagnosis at enrollment will be based on the site-determined values, except for the sensitivity analyses of the primary objective where presence of LBBB needs to be confirmed by the ECG Core Lab.

4.1.2.3 Intention-to-treat and Sensitivity Analyses

An intention-to-treat (ITT) analysis will be performed and will serve as the primary analysis for all the objectives in this study. Based on the ITT principle, this analysis will include all randomized patients in the treatment groups to which they were randomly assigned, regardless of their adherence with the entry criteria, regardless of the treatment they actually received, and regardless of subsequent withdrawal from treatment or deviation from the protocol¹. With this being said, patients with noncompliance of randomization including permanent crossover to the other study arm will stay in the treatment arm they were originally randomized to in the primary ITT analysis. A permanent crossover means the programming will not be corrected to the original randomization assignment (CIP section 5.5).

In addition, two sensitivity analyses will be performed for the primary objective:

1. ITT analysis for randomized patients whose presence of LBBB is confirmed by the ECG Core Lab. In this sensitivity analysis, patients with noncompliance of randomization including permanent crossovers will stay in the treatment arm they were originally randomized to per the ITT principle.
2. As-treated analysis for randomized patients whose presence of LBBB is confirmed by the ECG Core Lab. In this sensitivity analysis, patients' actual aCRT programming will be a time-varying covariate that has 3 categories: ACRT ON, ACRT OFF, and Neither, counting from the time randomization programming is implemented. Patient with major eligibility violations discovered after randomization will be excluded. Patients with major protocol violations after randomization, such as being programmed permanently to a mode that deviated from original randomization assignment due to a system modification after randomization, will be censored at the time of protocol violations.

4.1.2.4 Subgroup Analysis/Poolability

Poolability

Site will be included as a random effect to account for the site-by-site variability in the primary analysis of the primary endpoint, and baseline characteristics will be adjusted for in an ancillary analysis. Descriptive statistics for the primary endpoint will be reported study-wide and by investigational sites. In the circumstance where the statistical model of the primary analysis cannot converge due to low enrollments of some sites, sites with less than 5 randomized subjects will be combined to "small sites" first within city; if it doesn't work, then within state (if applicable), country, geographic region, and continent in order. Once a combined site has at least 5 randomized subjects, a new combined site will be started at the same geographic level. If there is only one site with less than 5 randomized subjects left at one geographic level, this site will be combined to the nearest site at the same geographic level.

Subgroup analysis

Subgroup analysis of the primary efficacy endpoint will be performed for a limited number of pre-specified subgroups by testing the effect of treatment by subgroup interaction on primary endpoint. The subgroups include:

- Geography: US/Canada vs. International
- Age
- Gender: Males vs. Females
- QRS duration: $\leq 150\text{ms}$ vs. $> 150\text{ms}$
- AV conduction time: median as cutoff
- LBBB: Core Lab confirmed vs. Core Lab not confirmed
- NYHA class (in different model where NYHA class is a covariate not a stratification factor)
- HF etiology
- Renal dysfunction
- Diabetes

The treatment by subgroup interaction effects for the subgroup described above will be tested at $\alpha=0.05$. Adjustment for multiple comparisons will be done. The interaction effects, confidence intervals, and unadjusted p-values for multiple comparisons will be reported using a Forest plot.

Similar subgroup analysis may also apply to the two secondary endpoints that are contributed to the primary endpoint: all-cause mortality, and intervention for heart failure decompensation.

4.1.2.5 Ancillary Analysis for Covariates Adjustment

Ancillary analysis will be performed for the primary objective to adjust for subject characteristics collected at enrollment and baseline. Such analysis may also be considered for the first two secondary objectives that are components of the primary endpoint. Modeling selection and determination will be described in the corresponding sections for those objectives.

4.1.2.6 Missing Data

All the data collected from the study will be reported and unauthentic data (if any) will not be included in any analysis dataset. Details on how to handle missing data are provided in the following sections for all the study objectives.

4.1.3 Reports for which this Statistical Analysis Plan applies

This analysis plan shall apply to the final report and other study analyses. Analyses that are conducted for Data Monitoring Committee (DMC) meetings will use the methods from this analysis plan as guidance when applicable. Statistical analysis for study-related publications will not be limited to this plan.

This study includes DMC reports not associated with an interim analysis, DMC reports based on 3 interim analyses, and a final report. A set of analyses including primary ITT analysis, sensitivity analyses per LBBB and aCRT programming, subgroup analysis for interaction with treatment, and ancillary analysis for covariates adjustment have been described in section 4.1.2. The analyses to be conducted at each stage of the study may vary by report type and study objectives that are considered. Table 2 indicates the analyses for each study objective that we will be conducted for the different study reports. Contents of this table are subject to change, depending on the needs of the DMC or the study itself. Note that, in order to control for family-wise α level, confidence intervals and p values will not be provided in any non-interim DMC report.

Table 2: Analysis plan matrix – when, what and for which

	DMC Reports Non-Interim	DMC Report Interim	Final Report
Primary Objective	Primary Analysis Sensitivity Analysis	Primary Analysis Sensitivity Analysis Subgroup Analysis	Primary Analysis Sensitivity Analysis Subgroup Analysis Ancillary Analysis
Secondary Objective #1: all-cause mortality	Primary Analysis	Primary Analysis Sensitivity Analysis	Primary Analysis Sensitivity Analysis Subgroup Analysis Ancillary Analysis
Secondary Objective #2: HF events	Primary Analysis	Primary Analysis Sensitivity Analysis Recurrent Events	Primary Analysis Sensitivity Analysis Subgroup Analysis Recurrent Events

			Ancillary Analysis
Secondary Objective #3 - #7	None	Primary Analysis	Primary Analysis
Ancillary Objectives	None*	None*	Primary Analysis

* Except for Ancillary Objective #3 (cardiovascular adverse events) that will be summarized in these reports,

4.2 Interim Analysis Plan

[figure not shown]
Four analyses including three interim analyses and a final analysis are planned for the primary objective. The 3 interim analyses will follow a symmetric group sequential design using the alpha-spending methodology of Lan and DeMets² with O'Brien-Fleming³ type boundaries. Specifically, the cumulative alpha-spending function at the k^{th} look or analysis:

$$\alpha(t_k) = 2 - 2\Phi\left(\frac{Z_{\alpha/2}}{\sqrt{t_k}}\right)$$

where $k=1, 2, \dots, K$ and t_k is the information fraction at the k^{th} look, In the group sequential design for time-to-event endpoint, the information fraction at the k^{th} look can be defined as the cumulative count of events at the k^{th} look divided by the projected number of events at the final look.

The O'Brien-Fleming function was chosen because it conservatively preserves most of the type I error for the final analysis, and the conservation of type I error is desired due to the multiple endpoints and objectives of interest in this trial. The statistical stopping rules are illustrated in the figure below.

Figure 1: Statistical stopping boundaries

The horizontal axis shows the number of events, indicating the timing of interim analyses after 275, 550, and 825 events, and the final analysis when 1100 events are accrued. If at any interim analysis the standardized Z statistic for the primary objective is in the darker blue area with solid boundary line, the DMC may advise to stop the study claiming the null hypothesis is rejected. This corresponds to a cumulative α -level of 0.00002, 0.00304, 0.0193 and 0.05 spent at the subsequent stages (see section 5.1 “Error Spending Information” table). If the Z Statistic is in the lighter blue area with dashed boundary line, the DMC may advise to stop the study for futility.

In case the study is stopped for efficacy after an interim analysis, the secondary objectives will be analyzed using a family-wise type I error rate derived from a Pocock-type alpha-spending function. This corresponds to a cumulative α -level of 0.018, 0.031, 0.041 and 0.05 spent at the subsequent stages⁴. Hommel procedure will be used to correct for multiplicity.⁵ This will be implemented by the SAS MULTTEST procedure.

Planned interim analyses, and any unplanned interim analyses, will be conducted under the auspices of the DMC assigned to this study. Medtronic will use the FDA recommended guidance entitled Establishment and Operation of Clinical Trial Data Monitoring Committees⁶ to guide interim statistical analyses and DMC operations. Interim analyses reports will be prepared by a Medtronic statistician and SAS programmers who are

members of the study team and are unblinded to randomization . A Medtronic statistician otherwise not involved in the study will perform validation. The lead statistician and all other Medtronic personnel will be blinded to interim analyses. The DMC is authorized to review unblinded interim analyses. The DMC will disseminate interim results only if absolutely necessary. Study centers will not receive information about interim results unless they need to know for the safety of their subjects.

Data review by the DMC that occurs between interim/final analyses will not spend type I error rate on the primary objective because there is a mutual agreement between the study team and DMC that no p values will be provided for any non-interim/final analysis and DMC will not make any decision on trial continuation or termination based on the results of such analysis. Early DMC meetings will monitor adverse events for unexpected risks to the study subjects and the overall conduct of the study. For each meeting, the DMC will be provided with information about enrollment rates, eligibility, baseline characteristics, and adverse events. The DMC will also be provided with information about the primary endpoint and its components. The planned subgroup analyses will be reported so that the DMC may examine futility in these subgroups. In order to stop the study earlier than planned, priority will be given to ensuring that there is sufficient information to assess cost-effectiveness. In addition, this assessment will balance the evidence at the interim analysis about the primary objective and secondary objectives #1 and #2. According to the DMC Charter, "Should the DMC recommend terminating the study early or recommend significant changes to the protocol, the SC and Medtronic may then be unblinded to the data if deemed necessary by the DMC. Any such dissemination of unblinded data will be documented and described in the final study report [...] The DMC will need to consider the level of completeness and adjudication status of the study at the moment of advice. Especially, in case of a recommendation to stop the study, the DMC will propose an implementation plan that accounts for the risk that completion of data cleaning and adjudication may alter results."

Interim Database Freezes

For each analysis prepared for a DMC meeting and each interim analysis, a visit cutoff date will be defined. For regularly scheduled DMC meetings, the visit cutoff date will be defined to allow time for data cleaning and analysis prior to the DMC meeting. A received cutoff date will also be declared prior to each DMC-related database freeze. Only Case Report Forms dated before the determined visit cutoff date and saved complete in the study database prior to the received cutoff date will be included in each DMC analysis.

Events that would trigger an interim analysis should be adjudicated. This will be subject to a time lag associated with the activities leading up to adjudication, including the site entering the information into the study database and saving as complete, the information about the event being sent to the Endpoint Adjudication Committee (EAC) (which will typically be sent within a batch) and the event being adjudicated and its adjudication results saved into the study database. EAC meetings occur on a regular basis in order to ensure that the percentage of adjudicated events is high.

When the number of patients with any adjudicated events comes close to the target of an interim analysis (275, 550 and 825 events for the 1st, 2nd and 3rd interim analysis, respectively), a DMC meeting for the interim analysis will be scheduled. The visit cutoff date will be about 6 weeks before the DMC meeting. It will be strived for to have all events that occurred prior to the visit cutoff date adjudicated. The received cutoff date will be right after the completion of adjudication for all the events, or 2 weeks before the meeting at the

latest. The database freeze date should be no later than 2 weeks after the received cutoff date. Note that the number of events before the database freeze might not be exactly the same as the target for an interim analysis. In such a case, an updated α -value for the interim analysis will be calculated using the SAS SEQTEST procedure accordingly. To foresee what is coming based on the best available information of the trial, the same analysis will be applied to all the primary events per investigators' evaluation in the interim analysis database. This will be done regardless of the adjudication status of those events.

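### The spending function printed in SAP 4.2 yields the listed cumulative alpha levels only if it is applied per side at 0.025 and doubled, a step the SAP does not state

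*SAP*

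**What the plan says.** SAP 4.2 describes a "symmetric group sequential design using the alpha-spending methodology" of Lan and DeMets with O'Brien-Fleming-type boundaries. It then makes this concrete ("Specifically, the cumulative alpha-spending function at the" k-th look) with the formula α(t_k) = 2 − 2Φ(Z_{α/2}/√t_k). The information fraction t_k is the cumulative event count "divided by the projected number of events at the final look", and the looks are fixed by the "timing of interim analyses after 275, 550, and 825 events, and the final analysis when 1100 events are accrued".

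The same section gives the cumulative levels as "0.00002, 0.00304, 0.0193 and 0.05 spent at the subsequent stages" and refers to an error-spending table in SAP 5.1 that is blacked out in the public copy. Protocol 11.4 lists the same four levels, and SAP 4.3.2, 4.3.4 and 4.3.6 repeat them. SAP 4.1 sets out to "preserve an overall two-sided alpha level of 0.05". The design code in SAP 4.3.8 has alpha 0.05, a two-sided alternative, four stages, the error-spending O'Brien-Fleming method, and stopping for both efficacy and futility.

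If the event count at an interim look misses its target, SAP 4.2 says an updated level "will be calculated using the SAS SEQTEST procedure accordingly". No visible text says whether α in the formula is the overall 0.05 or 0.025 per side.

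**The concern.** The formula and the list sit in the same section and are presented as the same rule. The printed function returns its own α at t = 1, so to end at the listed 0.05 it must be read with α = 0.05. On that reading it spends more alpha at each of the three interim looks than the list allows.

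This matters because recalculation is expected. SAP 4.2 accepts that the event count may miss its target, and SAP 4.3.2 says the actual level will depend on the actual number of events without naming a procedure there. The formula is the only printed link between an event count and a cumulative level. SAP 4.2 also requires validation by a statistician otherwise not involved in the study. A validator working from the formula would not reproduce a correct boundary, and the disagreement would have to be settled with unblinded interim data in hand.

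**Working it through.** **Inputs.** Overall alpha 0.05 two-sided (SAP 4.1, 4.3.8). Looks at 275, 550, 825 and 1100 events (SAP 4.2), so t = 0.25, 0.50, 0.75 and 1.00. Normal quantiles: z at 0.025 is 1.960; z at 0.0125 is 2.241.

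**Step 1. Reproduce the listed levels.** Apply the printed function to each side with α = 0.025, then double, which is 4 − 4Φ(2.241/√t):

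- t = 0.25: 2.241/0.500 = 4.483; per side 0.0000074; doubled 0.000015
- t = 0.50: 2.241/0.707 = 3.170; per side 0.001525; doubled 0.00305
- t = 0.75: 2.241/0.866 = 2.588; per side 0.00965; doubled 0.0193
- t = 1.00: 2.241; per side 0.025; doubled 0.05

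This matches the list to within 0.00001. At look 2 the list has 0.00304 and the calculation 0.00305. That is probably rounding in the software output, but it cannot be confirmed because SAP 5.1 is blacked out.

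**Step 2. Apply the printed formula as it stands, α = 0.05.** 2 − 2Φ(1.960/√t):

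- t = 0.25: 1.960/0.500 = 3.920; 0.000089
- t = 0.50: 1.960/0.707 = 2.772; 0.00557
- t = 0.75: 1.960/0.866 = 2.263; 0.0236
- t = 1.00: 1.960; 0.05

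**Step 3. Compare.**

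| Look (events) | Listed | Formula, α = 0.05 | Ratio to listed | Per side, doubled |
|---|---|---|---|---|
| 1 (275) | 0.00002 | 0.000089 | 4.4 | 0.000015 |
| 2 (550) | 0.00304 | 0.00557 | 1.83 | 0.00305 |
| 3 (825) | 0.0193 | 0.0236 | 1.22 | 0.0193 |
| 4 (1100) | 0.05 | 0.05 | 1.00 | 0.05 |

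**Step 4. Translate into boundaries.** Recursive numerical integration, efficacy bounds only:

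| Look | Z, formula | Z, per side | Nominal p, formula | Nominal p, per side |
|---|---|---|---|---|
| 1 | 3.920 | 4.333 | 0.000089 | 0.000015 |
| 2 | 2.774 | 2.963 | 0.0055 | 0.0030 |
| 3 | 2.298 | 2.359 | 0.0215 | 0.0183 |
| 4 | 2.043 | 2.014 | 0.0411 | 0.0440 |

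At look 2 the observed hazard ratio needed, exp(−2Z/√550), is about 0.789 with the formula and 0.777 per side. By simulation at the design hazard ratio of 0.818, the chance of crossing by look 2 is 34% against 27%, and overall power is 90.7% against 91.0%.

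**Step 5. Sensitivity to futility.** The code stops for both reasons, but how the futility bound enters the final boundary is not visible. If a binding O'Brien-Fleming-type futility bound with beta 0.10 is assumed, the first two efficacy boundaries do not change. The final nominal p becomes about 0.050 per side and about 0.047 with the formula, in place of 0.0440 and 0.0411.

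**Step 6. An off-target look (assumed for illustration: 560 events).** With t = 560/1100 = 0.509, the formula gives 0.0060 and the per-side rule 0.0034.

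**The case against.** The strongest reply is that the documents contain one set of decision levels, not two. The four listed values recur unchanged in Protocol 11.4 and SAP 4.2, 4.3.2, 4.3.4 and 4.3.6; no section states 0.0056 or 0.0236. They are what the printed function gives when 0.025 is spent on each side, which is natural for a symmetric two-sided design and agrees with the code in SAP 4.3.8. SAP 4.2 assigns interim recalculation to SEQTEST, and the formula has no operational role. Protocol Appendix C also makes the boundaries guidelines for the DMC, so no p-value stops the trial by itself.

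Most of this stands. A reader might infer that the SAP sets two competing efficacy thresholds, or that the listed levels are wrong; the documents support neither. A reader might also infer that a final p of 0.042 would succeed under one rule and fail under the other. That holds only if the futility bound is ignored or non-binding; under the binding bound assumed above, 0.042 succeeds under both.

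What the reply does not remove is that the formula, with the only overall alpha the SAP states, contradicts the levels beside it. Nothing visible states the per-side step or says which prevails if SEQTEST and the formula disagree, and the SEQTEST sentence covers interim analyses only.

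**Conclusion.** This is a real but modest inconsistency. Read with α = 0.05, the printed function overstates the listed cumulative alpha 4.4-fold, 1.83-fold and 1.22-fold at looks 1 to 3 and agrees at the final look. The listed levels are almost certainly the intended rule and can stand. Type I error is not inflated: both readings spend 0.05 in total, and power differs by 0.3 percentage points (91.0% − 90.7%, efficacy bounds only). The practical exposure is a boundary recomputed or validated from the printed text, most plausibly at the second look, where the nominal threshold would be about 0.0055 instead of 0.0030.

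The cumulative-alpha comparison needs only the printed formula, the stated alpha and the planned event counts. The boundary and power figures in step 4 also leave out futility. The size of any final-look difference depends on how the futility bound is handled, which the visible text does not settle.

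**What to change.** In SAP 4.2, do one of the following:

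- replace the formula with α(t) = 4 − 4Φ(z_{α/4}/√t), with α = 0.05 defined as the overall two-sided level; or
- keep the formula and add that it is applied to each side with α = 0.025, and that the listed levels are the two-sided sums.

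Then extend the SEQTEST sentence in SAP 4.2 so that the same function and procedure also govern the final analysis at its actual event count, and point SAP 4.3.2 to it.

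The cost is one or two lines of SAP text. The listed levels, the 1100-event target, the sample size and the design code are unchanged.
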